The Stage 1 cross sectional study will investigate two groups of people with dementia aged 60-89 years with 385 people in each group. Group 1 will comprise people living at home and Group 2 will comprise people living in care homes. The sample size has been calculated to allow detection of a prevalence of 50% with 5% precision and 95% confidence based on the reported estimated prevalence of VI in the population (5, 26). Subjects will be recruited through Memory Clinics and Old Age Psychiatry clinics in NHS trusts and through general medical practices with the assistance of DeNDRoN and Local Coordinating Research Networks. Additionally, Group 1 subjects will be recruited through Alzheimers Society local groups and Group 2 subjects will be recruited through direct contact with care homes. Where participants are recruited via AS, they will only be recruited from groups of service users for whom a medical diagnosis of dementia has been confirmed through the AS processes. It should also be noted that recruitment through AS is not intended to be the primary route, but rather an additional source of participants to enhance the overall recruitment strategy. BUPA

has offered to support the study but we will also recruit through other care providers to reduce the risk of selection bias. Further subjects for both groups, especially those living at home, can also be recruited through The Outside Clinic, one of the UK's leading providers of domiciliary eye care services. They have informed us that they test approximately 2,500 people with dementia each year (living in their own homes and in care homes).

Strategy: The team is aware that recruitment of people with dementia into research studies is not easy and we have adopted a multilayered approach to recruitment. It is intended that the majority of subjects for the prevalence study will be recruited with the assistance of regional DeNDRoNs and CLRNs.

DeNDRoN is launching the ENRICH research ready-care home network this year and we will make use of this to recruit participants.

Identification procedures

Potential participants with dementia will be identified from their medical records by the direct care team or by DeNDRoN or Local Coordinating Research staff who are frequently embedded in NHS clinics. In addition DeNDRoN maintain case registers of patients with dementia who are willing to participate in research and suitable participants who are on this register will be identified and approached.

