Additionally, individual face-to-face interviews will be sought with people with dementia who are able to consent to interview. Interviews will continue until no new data is being generated. Qualitative studies usually achieve saturation with 30 subjects (28) and this is the number envisaged in this study although recruitment will continue beyond 30 subjects if necessary.

Setting/ context

In Stage 1, subjects will be randomly recruited from multiple sites in four centres in England: London, Thames Valley, East Anglia and the North East to reflect demographic differences such as city, urban and rural settings and to encourage inclusion of people from a range of black and minority ethnic populations. We will recruit from multiple sites within each region. Regional Network Coordinators were contacted at the proposal development stage; they did an initial canvas for support which revealed widespread interest from local PIs and feedback that the study would be likely to be popular with patients and carers given the practical and widespread applicability of the topic.

Difficulties in recruiting people from black and minority ethnic groups were addressed in feedback to reviewers following submission of the full proposal. Our strategy aims to recruit subjects from a range of geographic areas to include a demographic mix of inner city, urban and rural areas. We will purposely seek to recruit subjects from BME groups in city populations where the ethnic populations are greatest e.g. London (North Thames), Leicester (Thames Valley). We have also approached the Primary Care Research Network in Central England (PCRN-CE) which has offered to approach GPs across their area to identify BME patients who could be invited to participate in the study.

The Stage 2 focus groups and individual face-to-face interviews with people with dementia will also be held in the same four centres.

Data collection

Stage 1: The subject will have a full optometric examination in line with requirements of the GOS sight test for people aged 60 years and over and the College of Optometrists' guideline CO4: *Examining the patient with dementia or other acquired cognitive impairment*.

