Stage 2: Data will be collected from focus groups of eye care professionals, family carers and professional (paid) carers and interviews with people with dementia. The focus group question schedule will be semi structured and cover participants' understanding of eye care for people with dementia; expectations of the eye examination; experience of eye examination and eye care of people with dementia; barriers encountered; and facilitators and strategies to improve eye care. Data obtained in each interview will depend on the individual's ability to recall, communicate and comprehend and will vary according to the degree of dementia.

Data analysis

Stage 1 – prevalence, along with their 95% confidence intervals, of VI due to refractive error, cataract, age-related macular degeneration, glaucoma and diabetic retinopathy will be established. These Confidence Intervals will be used to compare the prevalence of the VIs with published figures in the general population. Prevalence levels between people living at home and people living in care homes will be compared using tests for two independent proportions. Proportions of both previously undetected cases and detected but inappropriately managed cases will also be compared between people living at home and in care homes.

Missing data:

Our primary research objective was to measure the prevalence of a range of vision problems in a generic sample of people with dementia aged 60 to 89 years. The study is adequately powered to achieve this objective. The use of two groups of subjects is mainly to allow us to identify any differences in the level of undetected or inappropriately managed visual impairment between the two groups. This will inform Stage 2 of our study, in which we will investigate the reasons for any undetected or inappropriately managed visual impairment.

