Our sample size of 385 subjects in each group is based on an estimated prevalence of 50% with 5% precision and 95% confidence. This figure of 50% was the highest prevalence quoted in the literature for one of our target conditions. If the prevalence of a condition is either greater than or less than 50% then the study will require a sample size smaller than 385. We had anticipated that in a study of this nature there would be some missing data for each of the optometric tests as some of the participants/patients will be unable to perform them. There is no published data on the percentage of those with dementia who will be able to perform successfully individual elements of an eye examination. In the absence of published data we

took the view when writing our proposal that even if as few as 50% of subjects were able to complete a particular test with a prevalence of 50% (the worst case analysis) we would still have data from 385 subjects (50% of our total of 770), which is sufficient to generate a reliable estimate of the overall prevalence for the condition in a generic sample of patients with dementia.

Following the request for more detail on the impact of missing data we have consulted with a number of optometrists with extensive experience of eye examinations conducted on patients with dementia. Based on their responses we have quoted in Section 2 above (Testing people with dementia) estimates for the percentage of patients with dementia who are likely to be able to complete each test. The lowest percentage they estimate is 60%, compared with our worst case figure of 50% which was the figure used for our sample size calculation. Furthermore, these estimates suggest that, not only does our study have sufficient power to be able to generate a reliable generic figure for prevalence in dementia for each of our target conditions, but also that we should have sample sizes that are sufficiently large to allow statistical testing of differences in prevalence between our two groups (care home residents versus those living at home) for at least two thirds of the target conditions.

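### The overall prevalence is claimed for dementia in general but rests on a fixed 1:1 home/care-home quota, with no real split, weight or justification given

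*Protocol*

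**What the plan says.** The Sampling section plans "two groups of people with dementia aged 60-89 years with 385 people in each group", one drawn from private homes and the other from care-home residents. In the Data analysis section, under Missing data, the primary objective is to "measure the prevalence of a range of vision problems in a generic sample of people with dementia aged 60 to 89 years". The same paragraph explains the grouping: "The use of two groups of subjects is mainly to allow us to identify any differences in the level of undetected or inappropriately managed" (the object being visual impairment, compared across the settings). The size is justified as follows: "Our sample size of 385 subjects in each group is based on an estimated prevalence of 50% with 5% precision and 95% confidence". The protocol then argues that, even at 50% test completion, the 385 completers out of 770 would be "sufficient to generate a reliable estimate of the overall prevalence for the condition in a generic sample of patients with dementia".

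The Data analysis section also compares the prevalence confidence intervals with published general-population figures, and tests prevalence between the two settings.

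**The concern.** The 1:1 ratio was chosen mainly for a comparison between settings, yet the combined completers are then treated as if they represented people with dementia as a whole. The two readings agree only if half of people with dementia aged 60–89 live in care homes, or if prevalence is the same in both settings. The protocol supports neither condition.

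It gives reasons to doubt equal prevalence. Aims and objectives, and again Background, list research setting (care-home residents or not) among the reasons why earlier prevalence data are inconclusive. Background also cites a relative risk of 3.3 for care-home admission with loss of vision. That ratio is not stated to be specific to dementia and concerns admission, so it suggests a direction more than a size.

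The overall figure carries weight. Objective 2 and the Need section use prevalence to judge whether vision problems are more common in dementia than in older people generally, and Need promises generalisable findings for commissioners. If most people with dementia live at home and prevalence is higher in care homes, an unweighted 1:1 pool is pushed towards the answer that prevalence is higher.

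**Working it through.** **Inputs from the protocol.** 385 per group, 770 in total (Sampling); prevalence 50%, precision 5 points, 95% confidence, and a worst case of 385 completers from both groups together (Missing data).

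**Assumptions, because the protocol gives no values.** Share living at home w = 0.6, 0.7 or 0.8 (0.65 for one weighting example); gap between settings of 5, 10 or 20 points.

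**1. The plan's own figure.** n = z² p(1 − p)/d² = 1.96² × 0.25/0.05² = 384.15 with unrounded z, rounded up to 385. This reproduces. The half-width is 4.99 points at n = 385 and 3.53 at n = 770. The arithmetic is right; the question is which population it describes.

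**2. Bias of the unweighted pool, equal completion.** Population value: w·p_home + (1 − w)·p_care. Pool: 0.5·p_home + 0.5·p_care. Bias = pool − population = (w − 0.5)(p_care − p_home). In percentage points:

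| Gap p_care − p_home | w = 0.6 | w = 0.7 | w = 0.8 |
|---|---|---|---|
| 5 points | 0.5 | 1.0 | 1.5 |
| 10 points | 1.0 | 2.0 | 3.0 |
| 20 points | 2.0 | 4.0 | 6.0 |

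The bias is zero if w = 0.5 or the gap is zero, and it changes sign if either w − 0.5 or the gap does.

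**3. Effect on the interval.** Take w = 0.7.
- 45% at home, 55% in care homes: population 0.7 × 45 + 0.3 × 55 = 48%, pool 50%, bias 2 points. Coverage of the nominal 95% interval is about 88% with 385 completers and 80% with 770.
- 40% and 60%: population 0.7 × 40 + 0.3 × 60 = 46%, pool 50%, bias 4 points. Coverage is about 65% and 40%.

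**4. Unequal completion.** With equal group sizes the home share among completers is h = c_home/(c_home + c_care), and the bias becomes (w − h)(p_care − p_home). Take 40% and 60% with w = 0.65, so the population value is 0.65 × 40 + 0.35 × 60 = 47%.
- Completion 75% at home, 45% in care homes: pool = (0.75 × 40 + 0.45 × 60)/1.20 = 47.5%, bias 0.5 points.
- Completion reversed: pool = (0.45 × 40 + 0.75 × 60)/1.20 = 52.5%, bias 5.5 points.

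With equal completion the bias would be 50 − 47 = 3 points. Unequal completion can therefore shrink the bias or enlarge it. It can also differ from test to test, so different conditions may be averaged over different mixes.

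**5. Precision of a weighted figure.** At 50% prevalence, with completers split evenly, the variance is multiplied by 2[w² + (1 − w)²].
- w = 0.65: factor 2(0.4225 + 0.1225) = 1.09. The half-width at 385 is 4.99 × √1.09 = 5.2 points; 384.15 × 1.09 = 418.7, so 419 completers are needed for 5 points. At 770 the half-width is 3.53 × √1.09 = 3.7.
- w = 0.6, 0.7, 0.8: half-widths at 385 are 5.09, 5.38 and 5.82 points; completers needed are 400, 446 and 523.

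**The case against.** The strongest reply is that the protocol never says the overall estimate will be unweighted, and that weighting by residence is the kind of detail an SAP settles. This is fair as far as the estimator goes. But the protocol does fix a claim: a simple one-sample count of pooled completers suffices for the overall figure. If the pool is unweighted, the figure describes the achieved mix. If it is weighted, evenly split completers fall short of 5 points at 385 unless w = 0.5. The claim would hold with weighting only if completers happened to divide roughly as the population does.

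It can also be said that the setting-specific prevalences are unaffected, that each group was itself sized at 385, and that a weighted figure can be derived later without any design change. All of this stands, and it makes the repair cheap.

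A reader might infer more than the documents support:
- **That minority ethnic participants are oversampled.** Setting/ context says "We will purposely seek to recruit subjects from BME groups in city populations where the ethnic populations are greatest", but gives no quota or sampling fraction and mentions difficulty in recruiting these groups. The effort may only offset under-recruitment.
- **That unequal completion pulls the pool towards the home group and worsens the bias.** Completion is estimated only for the whole sample, and step 4 shows that a shift towards home can bring the pool closer to the truth.
- **That the study expects the settings to differ.** It plans to test for a difference; it states no direction or size.

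**Conclusion.** The point holds. Completers from a 1:1 residence quota are described as a generic dementia sample, and 385 of 770 are called sufficient for the overall prevalence, with nothing to link that mix to the population. The headline figure can be biased if the plan is followed as written.

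The size is unknown. Under the assumed shares and gaps it runs from 0.5 to 6 points, against a half-width of 4.99 points at 385 completers and 3.53 at 770. It would be too strong to say that the figure is biased whenever the settings differ: the true home share must also depart from the home share among completers. A small gap gives a small bias, and the 20-point rows are illustrations, not estimates.

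Nor does the point require the setting-specific prevalences to replace the stated primary objective. At 50% completion each group has about 192 completers and a half-width of about 7.1 points (1.96 × √(0.25/192.5)), which is a real loss of precision.

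**What to change.** In the Data analysis section:
- Define the overall prevalence as w·p_home + (1 − w)·p_care, with w taken from a cited home/care-home share for people with dementia aged 60–89. Use this figure in the comparison with general-population data.
- Use the stratified variance w²·p_home(1 − p_home)/n_home + (1 − w)²·p_care(1 − p_care)/n_care, where n_home and n_care are the completers of the relevant test in each setting.
- Show the result over a plausible range of w.
- Report the two setting-specific prevalences, with completion by setting for each test, beside the overall figure.
- Restate the precision under Missing data for the weighted estimate; for example, about 5.2 points at 385 completers split evenly with 65:35 weights, or 419 completers for 5 points.

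The cost is a slightly wider interval (at 65:35, from 5.0 to 5.2 points at 385 completers and from 3.5 to 3.7 at 770) and reliance on an external share. Recruitment does not change. Weighting removes the quota distortion only. It does not correct for selection through clinics, charity groups, care providers and a domiciliary eye-care provider, or for the requirement that participants have a carer or family member. The report should say so.

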2. Vision and Visual Acuity will be recorded using the Thomson Test Chart 2000 Lite, which allows the selection of letters or symbols which are most appropriate to the cognitive abilities of the patient. Test Chart 2000 Lite allows the presentation of standard LogMAR acuity tests, Snellen letters, Tumbling Es, Landolt Cs, and symbols. Furthermore, the choice of chart and size of letters/symbols presented to the patient can be altered at the touch of a button. The chart can be used at any test distance, so is ideal for domiciliary tests in rooms of varying dimensions.

It is estimated (based on consultation with optometrists with experience of working with people with dementia through the UK's leading provider of domiciliary eye care services) that at least 60% of our patients will be able to complete this Visual Acuity test, the results of which will allow us to identify the presence of visual impairment.

3. Binocular function will be assessed using the cover test and by testing ocular motility. In the cover test the optometrist observes the patient's eyes while one eye is covered in turn and then uncovered. The test allows for the detection of squint (strabismus) and other binocular vision anomalies. The cover test is carried out for both distance and near viewing, with the patient fixating a target. A range of fixation targets can be used on Test Chart 2000 in order to capture and hold the attention of the patient for tests that require steady eye and head position. For the motility test, which checks for any over- or under-action of the extra-ocular muscles, the patient is required to follow a moving light with their eyes while keeping their head still. Both cover test and motility should be possible for at least 60% of our patients. These tests are included in the eye examination but are not part of the battery of tests directly relevant to the research study.

4. Pupil reactions: The integrity of the pupillary pathways is assessed by shining a torch into each of the patient's eyes in turn. This objective test should be possible on the vast majority of patients. Testing pupil reactions is included in the eye examination but is not part of the battery of tests directly relevant to the study.

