5. The intraocular pressures (IOPs) will be measured using the iCare tonometer. This instrument is well accepted by patients. Although the test involves contact between a sterile probe and the patient's cornea, this contact is minimal and iCare tonometry does not require the use of a local anaesthetic. Tonometry is an objective measurement during which the only requirement from the patient is that they keep their eyes open and maintain reasonably steady fixation. The iCare tonometer is widely used in domiciliary testing by optometrists and acceptable agreement with the gold standard Goldmann Applanation Tonometer has been established in recent research (Jorge et al 2010).

It is estimated that tonometry will be possible on 90% of our patients and the results will contribute to the identification of glaucoma suspects and ocular hypertensives (patients with elevated IOP but no other signs of glaucoma).

6. The objective determination of refractive error (retinoscopy) will allow the strength of the patient's spectacle prescription to be determined. Retinoscopy is a technique which is used by optometrists in almost all eye examinations, and is attempted in all domiciliary tests. For retinoscopy the patient is required only to look into the distance at a light or other fixation target. The retinoscope beam of light is directed into the patient's eye and a proportion of this light is reflected from the back of the patient's eye and can be viewed in the patient's pupil (the retinoscope reflex). While viewing the reflex in the patient's pupil the optometrist uses lenses to modify the appearance of this reflex until an end point is reached (reversal).

The strength of lenses that produce the reversal end point allows the optometrist to measure the patient's refractive error. During retinoscopy the lenses will either be placed in a trial frame worn by the patient or, where necessary if poor co-operation dictates, be held by the optometrist in front of the patient's eyes.

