Wherever possible, this retinoscopy result will be modified subjectively with the patient reading letters or symbols presented on the test chart through different lenses selected by the optometrist in order to refine the retinoscopy result. The patient's Visual Acuity with the final spectacle prescription found by retinoscopy or subjective examination will be recorded. It is estimated that retinoscopy will be possible on 70% of our patients, with subjective refinement possible in most of these (50% of the total sample). These results will contribute to the identification of uncorrected refractive error and visual impairment.

7. Posterior eye examination: At this stage in the test the patient's pupils will normally be dilated using tropicamide eye drops to facilitate the examination of the eye's structures behind the iris, notably the lens, the retina and other back of the eye structures. Prior to pupillary dilation, the likelihood of the pupil dilation provoking an acute angle closure glaucoma (ACG) attack will be assessed using the pen light test for anterior chamber depth estimation (Elliott 2007). The risk of provoking an acute ACG attack with tropicamide is very low (Pandit and Taylor 2000, report zero cases of ACG in almost 4000 dilations). However, patients judged at risk of an ACG attack will not be dilated and will be examined through undilated pupils.

The tropicamide drops take approximately 15 - 20 minutes to produce a sufficiently dilated pupil. During this time the patient can have a break, if required, the examiner can complete the MMSE if necessary, the strength of any current glasses can be measured using a focimeter, and the external eyes can be examined using the ophthalmoscope. Once the pupils are fully dilated the examination of each eye follows using a direct hand held ophthalmoscope. The patient needs only to keep their eyes open and, if possible, to follow instructions as to where to direct their gaze. It is estimated that direct ophthalmoscopy will be possible on 85% of our patients and the results will contribute to the identification of cataract, AMD, diabetic retinopathy and glaucoma suspects.

As a further check on the possibility of a dilation-induced acute ACG attack, post-dilation IOPs will be measured using the iCare tonometer. A significant increase in IOP could be an indicator of a pending ACG attack and if this is suspected the optometrist will remain for a further hour and continue to monitor the patient.

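### At the 50% design prevalence, 385 per group gives ±5 points only with full test completion, and the claim that most conditions can be compared between groups is unsupported

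*Protocol*

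**What the plan says.** Under Sampling, Stage 1 enrols two groups "aged 60-89 years with 385 people in each group", one living at home and one in care homes, and "The sample size has been calculated to allow detection of a prevalence of 50% with 5% precision and 95% confidence". Data analysis, under Missing data, repeats this: "Our sample size of 385 subjects in each group is based on an estimated prevalence of 50% with 5% precision and 95% confidence".

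The same subsection then turns to non-completion. If only half the participants could do a test, "we would still have data from 385 subjects (50% of our total of 770"), which is judged enough for the overall prevalence. It also notes that a prevalence other than 50% would need fewer than 385.

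It goes on to say that the lowest completion estimate obtained from experienced optometrists is 60%, and infers that "we should have sample sizes that are sufficiently large to allow statistical testing of differences in prevalence between our two groups" for two thirds or more of the target conditions. It does not name those conditions.

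The test-by-test estimates are under Data collection:
- Step 2: "at least 60% of our patients will be able to complete this Visual Acuity test".
- Step 5: "It is estimated that tonometry will be possible on 90% of our patients".
- Step 6: "It is estimated that retinoscopy will be possible on 70% of our patients", with subjective refinement in 50% of the whole sample.
- Step 7: direct ophthalmoscopy in 85%.
- Step 8: visual fields in 20%.

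The Missing data text makes prevalence in one generic dementia sample the primary objective. It says the main reason for having two groups is to look for differences in undetected or badly managed visual impairment (VI).

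**The concern.** The number 385 does two jobs. It is first the requirement within each group, and then the number left when half of the pooled 770 complete a test. The second use justifies the pooled estimate. It says nothing about precision within a group, yet the text moves straight from it to comparing the groups.

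A sample size chosen for the precision of one proportion also does not show that two proportions can be compared usefully. That depends on the difference of interest, the error rates and the number completing in each group.

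At stake is how the setting comparison is read. If the protocol says the groups are large enough to test, a non-significant result may be reported as no difference between home and care home when only a sizeable difference could have been detected. The comparison is meant to inform Stage 2.

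**Working it through.** **Inputs.** Group size 385, total 770, design prevalence 50%, half-width 5 points, 95% confidence (Sampling; Missing data). Completion c: tonometry 90%, ophthalmoscopy 85%, retinoscopy 70%, acuity 60%, subjective refinement 50%, fields 20% (Data collection). Cited general-population prevalences: AMD 3.5%, glaucoma 3.3%, VI 14.3%, 30% and 50.5% (Background). Assumed here: two-sided 5% and 80% power, because the protocol states neither.

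**1. The plan's own figure.** n = 1.96² × 0.5 × 0.5 / 0.05² = 384.2, rounded up to 385. It reproduces exactly, with no allowance for non-completion.

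**2. Half-width at 50% prevalence.** Per group 1.96 × √(0.25 / (385c)); pooled 1.96 × √(0.25 / (770c)).

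| Test | c | Completers per group | Per-group half-width (points) | Pooled half-width (points) |
|---|---|---|---|---|
| Tonometry | 90% | 346.5 | 5.3 | 3.7 |
| Ophthalmoscopy | 85% | 327 | 5.4 | 3.8 |
| Retinoscopy | 70% | 269.5 | 6.0 | 4.2 |
| Acuity | 60% | 231 | 6.4 | 4.6 |
| Subjective refinement | 50% | 192.5 | 7.1 | 5.0 |
| Fields | 20% | 77 | 11.2 | 7.9 |

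No test reaches 5.0 within a group. Pooled, all do except fields.

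**3. Lower prevalence.** At 85% completion the per-group half-width for AMD is 1.96 × √(0.035 × 0.965 / 327) = 2.0 points, and for glaucoma at 3.3% it is 1.9. Five points per group is met for prevalences up to about 34% (c = 90%), 31% (85%), 23% (70%), 18% (60%), 15% (50%) and 5% (20%).

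**4. The completion floor.** Missing data gives 60% as the lowest estimate. Data collection gives 50% in step 6 and 20% in step 8.

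**5. What a between-group test could detect.** For n per group and p̄ = (p₁ + p₂)/2,

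power = Φ{ [ |p₂ − p₁|√n − 1.96√(2p̄(1 − p̄)) ] / √(p₁(1 − p₁) + p₂(1 − p₂)) }.

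Solving for 80% power:
- Upward from 50%: 10.0 points with all 385; 10.9 with 327; 12.0 with 269; 12.9 with 231.
- Glaucoma from 3.3% with 327 per group: a difference of 5.1 points, so 3.3% versus about 8.4%.

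Two illustrations: 45% versus 55% has 79% power with 385 per group and 58% with 231; 3.5% versus 7% has 52% with 327.

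**6. Undetected VI among cases.** If undetected VI is taken as a proportion of VI cases, the denominator is cases only. Cases per group = 231 × VI prevalence, assumed equal in both groups. For base rates of undetected VI from 20% to 50%:

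| Assumed VI prevalence | Cases per group | Detectable difference (points) |
|---|---|---|
| 14.3% | 231 × 0.143 = 33 | 32–34 |
| 30% | 231 × 0.30 = 69 | 22–24 |
| 50.5% | 231 × 0.505 = 117 | 16–18 |

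**The case against.** The protocol does handle non-completion for what it calls its primary objective. That objective is the pooled prevalence, and the 50% allowance works there for every test but fields, which only contribute to identifying glaucoma suspects. This stands. A reader might infer that the study is too small for its main aim; the figures do not support that.

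A reader might also infer that no test can ever give ±5 points within a group. That is wrong too. The shortfall belongs to the 50% design prevalence, which the protocol itself presents as the worst case, adding that other prevalences need fewer people. AMD and glaucoma at their cited rates are well inside 5 points. Narrow absolute precision does not rescue the comparison, though, as the 52% power for 3.5% versus 7% shows.

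It can further be said that the comparison sentence is hedged, concedes that some conditions fall short, names no difference of interest, and that power and detectable differences may be in an analysis plan not seen here. Leaving those details out would not be a fault. But the protocol makes a positive statement that the groups are large enough, and derives it from a completion minimum that its own text contradicts. That part remains whatever a later plan contains.

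Finally, whether 13 points is a large difference is a clinical judgement that the documents do not settle.

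**Conclusion.** The point holds in a limited form. At 50% prevalence the per-group half-width is 5.3 to 7.1 points for tests with 50% to 90% completion, and 11.2 for fields, against the 5 points used to size each group. The pooled estimate is sound apart from fields, and lower-prevalence conditions meet 5 points within a group.

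The statement that the groups can be compared for most conditions is unsupported. It has no two-sample basis and rests on a 60% floor that conflicts with the stated 50% and 20%. The detectable differences depend on the assumed two-sided 5% and 80% power. Those for undetected VI also depend heavily on VI prevalence, so the range of 16 to 34 points should be shown whole and no single value taken from it.

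This should be corrected, but it does not threaten the primary objective.

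**What to change.** 1. Under Sampling and Missing data, state that ±5 points at 50% prevalence with 50% completion applies to the pooled 770. Give per-group precision by test and by assumed prevalence; one blanket range would be wrong for AMD and glaucoma.
2. Reconcile the 60% minimum in Missing data with the 50% and 20% in Data collection, steps 6 and 8.
3. Replace the two-thirds statement with detectable differences under stated assumptions (two-sided 5%, 80% power): about 13 points from 50% with 231 per group; 3.3% versus about 8.4% with 327 per group; and, for undetected VI among cases, about 16–18, 22–24 or 32–34 points if VI prevalence is 50.5%, 30% or 14.3%.
4. Report between-group results as differences with 95% confidence intervals, and say that a non-significant result will not be read as no difference.

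The cost is wording only. The stated figures become less favourable; no extra recruitment is needed.
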